2.1. Study Rationale

Detailed information about the rationale for the selected doses can be found in Section 4.3 Justification for Dose.

Adults

In this study, safety and immunogenicity responses following 2-dose $(5x10^{10} \text{ vp}, 2.5x10^{10} \text{ vp}, 1.25x10^{10} \text{ vp})$ and single-dose $(5x10^{10} \text{ vp}, 1x10^{11} \text{ vp})$ primary vaccination regimens will be assessed in adults aged 18 to 55 years inclusive, and adults in good or stable health aged 65 years and older, to investigate dose sparing measures resulting in an increase of the number of vaccine doses available in a pandemic context. Safety and immunogenicity of 28-, 56-, and 84-day vaccination intervals for the 2-dose regimen $(5x10^{10} \text{ vp})$ will also be assessed to gather insight on the possible compression and delay of the vaccination schedule, as this may be of interest in an emergency use setting.

The $5x10^{10}$ vp dose level is administered in the Phase 3 efficacy studies VAC31518COV3001 (1-dose regimen) and VAC31518COV3009 (2-dose regimen).

In addition, an assessment of the immunogenicity of the 1.25×10^{10} vp Ad26.COV2.S dose level that is representative of the vaccine titer at the end of the foreseen shelf-life for the 5×10^{10} vp dose level in the context of emergency use with storage at 2-8 °C will be done. By lowering the dose level (ie, to 2.5×10^{10} vp and 1.25×10^{10} vp), there will also be a potential to immunobridge to a lower dose level regimen, should the efficacy study (VAC31518COV3001) provide evidence of an immune correlate of protection.

And finally, the anamnestic response after 7 days following a low-dose antigen presentation (1.25x10¹⁰ vp Ad26.COV2.S) as a surrogate of antigen exposure upon SARS-CoV-2 infection,

after the primary 2-dose or single-dose vaccination regimens, will be assessed in adult Groups 1-5, 7 and 9.

Adolescents

Available platform data, as well as safety data from the VAC31518COV1001 study, (see Section 2.2 and Section 2.3.1) support initiating evaluation of Ad26.COV2.S in adolescents aged 12 to 17 years, inclusive. In order to generate data in adolescents that will allow the use of a vaccine to prevent COVID-19 in this age group, the safety and immunogenicity responses following primary vaccination regimens will also be assessed in adolescents aged 12 to 17 years, inclusive.

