With implementation of protocol Amendment 5, participants who were initially enrolled to receive placebo (Groups 6, 8 and 10), will be offered a 2-dose (28-day interval) Ad26.COV2.S vaccination regimen at the 5x10¹⁰ vp dose level. In October 2020, the study was temporarily paused because one of the pausing rules was met in study COV3001. When the pause was lifted, most of the participants in Groups 7-8 had missed their visit window for Vaccination 2 (Visit 4), rendering the

intent of the 28-day vaccination interval in these groups futile. The goal in offering 2 doses of study vaccine to those participants who initially received placebo in this study is to recreate this 28-day vaccination interval, and to restore the objectives associated with this interval. The original 28-day interval target group was 75 participants. Hence the total number of placebo recipients from Groups 6, 8 and 10 (target n 75) is intended to fulfill the original target enrollment for Group 7.

With implementation of protocol Amendment 5, all adult participants will be unblinded to the primary vaccination regimen, and, adults who received placebo in the primary vaccine regimen, will receive a 2 dose active Ad26.COV2.S vaccine regimen at a 28-day interval and at a dose level of $5x10^{10}$ vp, in an open-label manner. Per group, approximately one third of participants will be 65 years and older.

Adult participants who received the active vaccine in the primary vaccine regimen will be followed up for 12 months after vaccination 2; adult participants who received placebo in the primary vaccine regimen will be followed up for 6 months after receipt of the unblinded vaccination 1 (ie, receipt of the first active vaccine following unblinding).

Groups 1-6

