400 participants (75 participants per active vaccine group, 25 in the placebo group) will be randomized in parallel in a 3:3:3:3:1 ratio to 1 of 6 vaccination groups. Participants will receive a 2-dose (56-day interval, Groups 1-3) vaccination regimen at different dose levels (5×10^{10} vp, 2.5×10^{10} vp, and 1.25×10^{10} vp) or single-dose vaccination regimen (Groups 4-5) at different dose levels (1×10^{11} vp, 5×10^{10} vp), or placebo (Group 6). For blinding purposes, participants in the single-dose groups (Groups 4-5) will receive a placebo vaccination on Day 57. Additional exploratory cellular immunogenicity evaluations (PBMC) will be performed in a subset of participants (21/group in Groups 1-5, 7 in Group 6; at selected sites). Participants in Group 6 who received 2-doses of placebo in the primary vaccine regimen will receive 2 doses of active vaccine at a single dose level of 5×10^{10} vp, at a 28-day interval.

Groups 7-8

75 participants (50 participants in the active vaccine group, 25 in the placebo group) will be randomized in parallel in a 2:1 ratio, to 1 of 2 vaccination groups. Participants will receive a 2 dose (28-day interval, Groups 7^a) vaccination regimen at a 5×10^{10} vp dose level or placebo (Group 8). Participants in Group 8 who received 2-doses of placebo in the primary vaccine regimen will receive 2 doses of active vaccine at a single dose level of 5×10^{10} vp, at a 28-day interval.

-

^a Group 7 and 8: only 2 subjects (one in each group) are vaccinated at a 28-day interval, due to a study pause

Groups 9-10

75 participants (50 participants in the active vaccine group, 25 in the placebo group) will be randomized in parallel in a 2:1 ratio, to 1 of 2 vaccination groups. Participants will receive a 2 dose (84-day interval, Group 9) vaccination regimen at a 5×10^{10} vp dose level or placebo (Group 10). Participants in Group 10 who received 2-doses of placebo in the primary vaccine regimen will receive 2 doses of active vaccine at a single dose level of 5×10^{10} vp, at a 28-day interval.

The vaccination schedules are presented in Table 2.

Table 2: Vaccination Schedules Adults

Adults ≥18 to ≤55 Years and ≥65 Years

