5.1.5. Analyses by groups and pooled across groups

All analyses are planned to be performed within each group separately, unless explicitly indicated that data will be pooled across groups.

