5.3. Primary Endpoint(s) Analysis

The primary endpoints in this study, are:

Adults

Humoral Immune Response

All participants in groups 1-3 (3 dose levels of Ad26.COVS.S administered as a 2-dose schedule at a 56-day interval):

- Serological response to vaccination as measured by virus neutralization assay (VNA) titers and enzyme-linked immunosorbent assay (S-ELISA EU/mL), 28 days after Vaccination 2.
- Antibody geometric mean titers (GMTs) (VNA) and geometric mean concentrations (GMCs) (S-ELISA), 28 days after Vaccination 2.

All participants in groups 4-5 (2 dose levels of Ad26.COVS.S administered as a single vaccination):

- Serological response to vaccination as measured by VNA titers and ELISA (S-ELISA EU/mL), 28 days after Vaccination 1.
- Antibody GMTs (VNA) and GMCs (S-ELISA), 28 days after Vaccination 1.

All participants in groups 7-9 (5×10^{10} vp dose level, administered as a 2-dose schedule at a 28-day and at an 84-day interval):

- Serological response to vaccination as measured by VNA titers and ELISA (S-ELISA EU/mL), 28 days after Vaccination 2.
- Antibody GMTs (VNA) and GMCs (S-ELISA), 28 days after Vaccination 2.

Safety and reactogenicity of Ad26.COVS.S

- Solicited local and systemic AEs for 7 days after each vaccination.
- Unsolicited AEs for 28 days after each vaccination.
- Serious adverse events (SAEs) and adverse events of special interest (AESIs) throughout the study (from first vaccination until end of the study)

Adolescents

Safety and reactogenicity of Ad26.COVS.S

- Solicited local and systemic AEs for 7 days after vaccination.
- Unsolicited AEs for 28 days after vaccination.
- SAEs (incl. Multisystem Inflammatory Syndrome in Children [MIS-C]) and AESIs throughout the study (from first vaccination until end of the study).

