5.7.1.6.2. Interval response modeling

To explore the interval duration effect of the double vaccination regimen, data from D28 post 2nd Vaccination of the groups 3, 7 and 9 will be analyzed using a regression model with log10 transformed VNA and ELISA results as dependent variable and interval duration as exploratory variable. Depending on the pattern observed a linear or non-linear model will be used.

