6.2. Appendix 2 Changes to Protocol-Planned Analyses

In October 2020, the current study was temporarily paused because one of the pausing rules was met in study COV3001. When the pause was lifted, most of the participants in Groups 7-8 had missed their visit window for Vaccination 2, rendering the intent of the 28-day vaccination interval in these groups futile.

For safety analyses,

- the 2 subjects vaccinated before pausing rule (28-day interval) will only be shown in the listings.
- the other subjects received the vaccination 2 between 51 and 72 days after Vaccination 1. They will be integrated in the Full Analysis Set with groups 1 and 6 (56-day interval).

For immunogenicity analyses,

- subjects randomized in groups 7 and 8 won't be included in PPI set
- a modified PPI set will be defined as follows :
subjects with vaccination 2 within the window (54-64) or subjects who did not receive vaccination 2 will be integrated in groups 1 and 6
- a modified FAS set will be defined as follows :
subjects in mPPI set and subjects with vaccination 2 in (51-53) days or (65-72) days window

6.3. Appendix 3 Guidance for Industry: Toxicity Grading Scale for Healthy Adult and Adolescent Volunteers Enrolled in Preventive Vaccine Clinical Trials

The laboratory values provided in the tables below serve as guidelines and are dependent upon institutional normal parameters. Institutional normal reference ranges should be provided to demonstrate that they are appropriate.

If a laboratory value falls within the grading as specified below but also within the local laboratory normal limits, the value is considered as normal.

Serum *	Mild (Grade 1)	Moderate (Grade 2)	Severe (Grade 3)	Potentially Life Threatening (Grade 4)**
Sodium – Hyponatremia mEq/L	132 – 134	130 – 131	125 – 129	< 125
Sodium – Hypernatremia mEq/L	144 – 145	146 – 147	148 – 150	> 150
Potassium – Hyperkalemia mEq/L	5.1 – 5.2	5.3 – 5.4	5.5 – 5.6	> 5.6
Potassium – Hypokalemia mEq/L	3.5 – 3.6	3.3 – 3.4	3.1 – 3.2	< 3.1
Glucose – Hypoglycemia mg/dL	65 – 69	55 – 64	45 – 54	< 45
Glucose – Hyperglycemia Fasting – mg/dL Random – mg/dL	100 – 110 110 – 125	111 – 125 126 – 200	>125 >200	Insulin requirements or hyperosmolar coma
Blood Urea Nitrogen BUN mg/dL	23-26	27 – 31	> 31	Requires dialysis
Creatinine – mg/dL	1.5 – 1.7	1.8 – 2.0	2.1 – 2.5	> 2.5 or requires dialysis
Calcium – hypocalcemia mg/dL	8.0 – 8.4	7.5 – 7.9	7.0 – 7.4	< 7.0
Calcium – hypercalcemia mg/dL	10.5 – 11.0	11.1 – 11.5	11.6 – 12.0	> 12.0

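### The 28-day primary humoral endpoint and the interval model still rest on Group 7, which has no 28-day participants in the PPI, modified PPI or modified FAS; the cross-vaccinated groups meant to replace it are not named in either

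*SAP*

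**What the plan says.** Protocol section 3 keeps the 28-day, 5×10^10 vp two-dose schedule as an adult primary humoral objective. SAP 5.3 assigns the 28-day and 84-day endpoint to "All participants in groups 7-9". SAP 5.7.1.6.2 states that "data from D28 post 2nd Vaccination of the groups 3, 7 and 9 will be analyzed using a regression model", with interval duration as the regressor. Protocol 2.1 sets the interval question at one dose level, 5×10^10 vp: "Safety and immunogenicity of 28-, 56-, and 84-day vaccination intervals for the 2-dose regimen".

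The October 2020 pause undid the 28-day arm. The Protocol 4.1 footnote says that in Groups 7 and 8 "only 2 subjects (one in each group) are vaccinated at a 28-day interval, due to a study pause". SAP Appendix 2 responds in three steps for immunogenicity:

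- PPI: "subjects randomized in groups 7 and 8 won't be included in PPI set".
- Modified PPI: participants with Vaccination 2 at 54-64 days, or with no Vaccination 2, are counted with Groups 1 and 6.
- Modified FAS: "subjects in mPPI set and subjects with vaccination 2 in (51-53) days or (65-72) days window".

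Protocol 4.1 supplies a replacement. Placebo Groups 6, 8 and 10 (target 75) receive two open-label doses 28 days apart, and the stated goal "is to recreate this 28-day vaccination interval, and to restore the objectives associated with this interval". They are sampled 28 days after the second open-label dose (visit UB57). On pooling, SAP 5.1.5 says: "All analyses are planned to be performed within each group separately, unless explicitly indicated that data will be pooled across groups".

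**The concern.** These passages cannot all be carried out. The SAP was updated for Amendments 5 and 6 and defines cross-vaccination phases. But the primary endpoint list and the models still point to the group that the pause emptied, and Groups 6, 8 and 10 appear in the dose models only as placebo.

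Two things are at stake. First, the 28-day part of a stated primary endpoint has nobody in it in the main immunogenicity set, while the data collected to restore it have no primary role. In the FAS, a result headed 28-day could consist almost wholly of people dosed at 51-72 days. Second, the interval model names Group 3, whose dose level differs from that of Groups 7 and 9. Without Group 7, an apparent effect of a longer interval could be an effect of dose.

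**Working it through.** **Target size.** 25 + 25 + 25 (Groups 6, 8, 10) = 75, which reproduces the protocol's figure. The protocol also calls 75 the original 28-day target; that matches Groups 7 and 8 together (50 + 25), whereas Group 7 alone is 50.

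**Active participants at a true 28-day interval, original phase.** One Group 7 participant qualifies (Protocol 4.1 footnote).

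| Set | Rule | Active n at 28 days |
|---|---|---|
| PPI | all of Groups 7-8 excluded | 0 |
| Modified PPI | Vaccination 2 at 54-64 days, or none | 0 |
| Modified FAS | adds 51-53 and 65-72 days | 0 |
| FAS | at least one documented dose | at most 1 |

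Day 28 falls in none of the modified windows. Group 9 is unaffected and still fills the 84-day part of the endpoint.

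**Cross-vaccinated participants in the PPI.** The exclusion is by randomised group and carries no time limit. Read literally, it also drops Group 8's open-label samples, leaving at most 25 + 25 = 50 of 75.

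**Precision of a 28-day geometric mean.** The 95% CI multiplies and divides the estimate by 10^(t(0.975, n−1) × SD/√n). The documents give no SD; I assume a log10 SD of 0.4 to 0.5.

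| n | SD 0.4 | SD 0.5 |
|---|---|---|
| 25 (one group) | 1.46 | 1.61 |
| 50 (Groups 6 and 10) | 1.30 | 1.39 |
| 75 (all three) | 1.24 | 1.30 |

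**Interval model in the PPI and modified sets.** This takes Groups 3 and 9 as kept in all three sets, and Group 7 participants as counted with Group 1 in the modified FAS as they are in the modified PPI. What remains is Group 3 (56 days, 1.25×10^10 vp, planned 75) and Group 9 (84 days, 5×10^10 vp, planned 50). The SAP model has no dose term. To see whether interval could be separated from dose, add one: the rows (1, 56, log10 1.25×10^10) and (1, 84, log10 5×10^10) have rank 2 for 3 parameters. It cannot be separated. With two interval levels, curvature cannot be estimated either, although the SAP allows a non-linear model.

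**Size of the dose component.** If titer varies as dose^b, the 84-day to 56-day ratio is multiplied by (5/1.25)^b = 4^b. The exponent is an assumption: b = 0.1, 0.2 and 0.3 give 1.15, 1.32 and 1.52. The CI factor of that ratio is 10^(t(0.975, 123) × SD × √(1/75 + 1/50)) = 1.40 at SD 0.4 and 1.52 at SD 0.5. At the upper end of the range, the dose component is about as large as the sampling error.

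**Interval model in the FAS.** Appendix 2 merges the 51-72-day participants into Groups 1 and 6 of the FAS under its safety heading only. For immunogenicity they may therefore stay in Group 7. The rows are then Group 3 (56 days, low dose), Group 7 (51-72 days, 5×10^10 vp) and Group 9 (84 days, 5×10^10 vp), which has rank 3. Interval and dose could be separated if a dose term were fitted. The SAP's model has none, so it still mixes dose levels, and it has at most one active participant at 28 days.

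**The case against.** The strongest case against has four parts.

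1. **Nothing is tested.** Protocol 9.1 excludes formal hypothesis testing and SAP 5.7.1.6 calls the modeling explorative. This stands, and it limits the severity.
2. **Separation is partly deliberate.** Protocol 9.4.2 requires adult data after unblinding to be analysed separately, and Protocol 9.5 ties the primary analysis to Day 57 for Groups 7-8. This stands as a constraint on the fix. It does not explain why the 28-day endpoint still names Group 7 when the protocol says cross-vaccination is to restore that objective.
3. **The data are not lost.** A reader might infer that the cross-vaccinated samples go unanalysed. The documents do not support that: the secondary endpoint covering all groups at all blood collection timepoints (SAP 5.4.1) includes them. It does not, however, supply the primary 28-day estimate or repair the model.
4. **Pooling is not ruled out.** A reader might infer that the three groups must be shown separately. That is only the SAP 5.1.5 default. SAP 4 analyses by vaccine actually received, SAP 5.7.1 builds tables by planned regimen, and details are left to the Data Presentation Specifications. Pooling is unsettled rather than barred, which is a reason to state it.

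Two further stronger readings fail. Full dose-interval confounding in every analysis set is not supported, because of the FAS reading above. A firm count of cross-vaccinated participants in the modified FAS is not supported either, because Appendix 2 does not say whether Group 10 belongs to the modified sets.

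**Conclusion.** The point holds and should be fixed. The 28-day part of the primary humoral endpoint, as assigned, has 0 active participants in the PPI, modified PPI and modified FAS and at most 1 in the FAS. No primary endpoint or model names the post-cross-vaccination data of the 75 targeted replacements. In the three restricted sets, the interval model compares two groups that differ in both interval and dose; in the FAS the aliasing is incomplete, but dose levels are still mixed. The set counts follow from the documents. The CI factors rest on an assumed SD, the dose component on an assumed exponent, and all group sizes are targets without dropout. The consequence is a missing, mislabelled or confounded descriptive estimate. A reader might infer a false claim of effect or an error-rate problem, but no test or decision rule depends on these analyses.

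**What to change.** 1. **SAP 5.3.** Define the 28-day endpoint on cross-vaccinated Groups 6, 8 and 10 pooled at UB57, and state the pooling explicitly as SAP 5.1.5 requires. Label it open-label, non-randomised and specified after the primary-analysis unblinding, and report it at the final analysis. Name Group 9 alone for the 84-day endpoint. Conform the Day 57, Groups 7-8 wording in Protocol 9.5.
2. **SAP Appendix 2.** Limit the PPI exclusion of Groups 7-8 to their blinded-phase samples, so that up to 75 rather than 50 cross-vaccinated participants are eligible. State whether Group 10 belongs to the modified sets.
3. **SAP 5.7.1.6.2.** Remove Group 7 as the 28-day level. Reconcile Group 3 with the 5×10^10 vp interval objective in Protocol 2.1; Protocol Table 2 shows Group 1 as the 56-day two-dose group at that level. Show cross-vaccinated data only as a labelled supplementary, non-randomised fit or side-by-side description, so that post-unblinding data stay separate as Protocol 9.4.2 requires.
4. **Minor, SAP 5.7.1.5.1.** State that fold rise and responder status after cross-vaccination use the pre-dose UB1 sample. SAP 5.1.1 otherwise defaults to Day 1.

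The cost is wording in the SAP and one conforming change in Protocol 9.5. The UB1 and UB57 samples are already scheduled, so no visit, blood draw or assay is added. The price is that the 28-day result is non-randomised and arrives at the final analysis.
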